## 12.3. Procedures

### 12.3.1. All Adverse Events

All AEs and special reporting situations, whether serious or nonserious, will be reported from the time a signed and dated ICF is obtained until completion of the subject's last study-related procedure (which may include contact for follow-up of safety). SAEs, including those spontaneously reported to the investigator within 30 days after the last dose of study drug, must be reported using the Serious Adverse Event Form. The sponsor will evaluate any safety information that is spontaneously reported by an investigator beyond the time frame specified in the protocol.

Progression of symptoms associated with AD should not be recorded as an AE unless they are considered to be accelerated in the opinion of the investigator.

Adverse events of special interest ie, lightening of skin, lightening of hair and ophthalmologic AEs will be recorded on the AE eCRF page with a mark for AESI. For additional information on the reporting of AESIs refer to Attachment 2.

Anticipated adverse events may be recorded and reported based on local rules and regulations. A list of events considered anticipated events for the purposes of this study, and their reporting requirements can be found in Attachment 1.

All AEs, regardless of seriousness, severity, or presumed relationship to study drug, must be recorded using medical terminology in the source document and the eCRF. Whenever possible, diagnoses should be given when signs and symptoms are due to a common etiology (eg, cough, runny nose, sneezing, sore throat, and head congestion should be reported as “upper respiratory infection”). Investigators must record in the eCRF their opinion concerning the relationship of the AE to study therapy. All measures required for AE management must be recorded in the source document and reported according to sponsor instructions.

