**Attachment 2: Adverse Events of Special Interest**

The following events are considered to be events of special interest:

- Lightening of skin
- Lightening of hair
- Ophthalmologic adverse events (AEs)

Cases of lightening of skin or lightening of hair should result in dermatological consultation with digital photography of the findings either by the dermatologist or a qualified designee.

For all initial reports of ophthalmologic AEs investigational sites should contact the sponsor's medical monitor for further follow-up.

All initial reports of treatment-emergent lightening of skin or hair, or treatment-emergent ophthalmologic AEs must be reported to the sponsor by the investigational staff within 24 hours of their knowledge of the event even if these events do not meet the definition of an SAE.

If these are deemed AEs, the site is to record these events on the AE eCRF page checked as AESI. If determined to be a serious adverse event (SAE) follow reporting as outlined in Section [12.3.2](#).

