6.1 Adverse Events

The verbatim terms used in the CRF by investigators to identify adverse events will be coded using the Medical Dictionary for Regulatory Activities (MedDRA). Any AE occurring on or after the date of the initial administration of study medication through the day of last dose plus 7 days is considered to be treatment emergent. If the event date is recorded as partial or completely missing, then the event will be considered to be treatment emergent unless it is known to be prior to the first administration of study medication based on a partial onset date or resolution date. All reported treatment-emergent adverse events will be included in the analysis. For each adverse event, the number and percentage of subjects who experience at least 1 occurrence of the given event will be summarized by treatment group. AEs in the off-treatment period are the AEs with onset more than 7 days after the last dosing.

Summary tables will be provided for:

- AEs
- AEs with a fatal outcome

- Serious AEs (SAEs)
- AEs leading to discontinuation of study medication (events with action taken of ‘drug withdrawn’)
- AEs leading to termination of study participation (events associated with a trial termination reason of ‘adverse event’)
- AEs by severity

AEs will also be summarized by age group, by gender, and by race. In addition to the summary tables, listings will be provided for subjects who:

- Died
- Had SAEs
- Had AEs leading to discontinuation of study medication or termination of study participation

The above listings will include events with onset during the screening phase.

Incidence of other treatment-emergent adverse events of special interest will be summarized. Hypopigmentation related and retinal related adverse events are identified by the investigator on the AE eCRF page and include:

- Hypopigmentation Related Adverse Events
 - Hair and skin hypopigmentation (events related to lighting hair, skin coloration, or iris coloration)
- Retinal Related Adverse Events
 - Retinal changes

Hepatic related treatment-emergent adverse events will also be summarized. Adverse events related to abnormal LFTs are defined as follows:

Events belonging to the MedDRA Drug Related Hepatic disorders SMQ – comprehensive search

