In addition, other adverse event clinical MedDRA PT clusters will be summarized by treatment during the on-treatment phase and off-treatment phase of the study (including but not limited to rash related, sleep disorder related, depression related, anxiety related adverse events).

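### SAP 6.1 counts hypopigmentation and retinal AESIs only when the investigator marks them, so an unmarked coded event is absent from the AESI table; its eye category is also narrower than the protocol's.

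*SAP*

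**What the plan says.** SAP 6.1 Adverse Events plans a table for these events: "Incidence of other treatment-emergent adverse events of special interest will be summarized". It then gives the identification rule: "Hypopigmentation related and retinal related adverse events are identified by the investigator on the AE eCRF page and include" two groups. One is hypopigmentation, meaning colour change of hair, skin or iris. The other is retinal changes.

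The protocol shows what identification on the page means. Section 12.3.1 says that "lightening of hair and ophthalmologic AEs will be recorded on the AE eCRF page with a mark for AESI". Attachment 2 says that, once a finding is judged to be an adverse event, "the site is to record these events on the AE eCRF page checked as AESI".

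The same SAP section codes all adverse events in MedDRA and uses coded terms for other groups. Hepatic events are "Events belonging to the MedDRA Drug Related Hepatic disorders SMQ", with a comprehensive search. Further preferred-term clusters are planned, "including but not limited to rash related, sleep disorder related, depression related, anxiety related adverse events".

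**The concern.** The protocol singles out lightening of skin, lightening of hair and ophthalmologic events for special attention. In the SAP these are the named event groups whose count depends on a site ticking a box. If a site reports, say, a hair-colour change and the term is coded but the box is left empty, the event does not count as an AESI.

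Safety summaries are a main remaining output now that dosing has stopped (SAP Section 1). A reader who wants the number of subjects per arm with any pigment or eye event will go to the AESI table. If qualifying events were left unmarked, that table gives too low a number and nothing in it shows this.

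The eye category raises a second question. A marked eye event that is neither retinal nor a change of iris colour is an AESI under the protocol but has no stated place in the SAP's two groups.

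**Working it through.** The plan states no figure for this point, so there is none to reproduce. The check is a comparison of the text, followed by a short statement of what the rule counts.

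**1. Routes into the AESI table**
- Investigator mark: yes (SAP 6.1; Protocol 12.3.1 and Attachment 2).
- Coded term, standardised query or term list for pigment or eye events: none in either document.
- Reconciliation of marks with coded terms, or with the expedited reports sent to the sponsor: none described.
- Protocol 11.10: says only that subjects with AESIs may be counted or listed. It defines no search.

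The mark is therefore the only stated route.

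**2. Where an unmarked qualifying event still appears**
- General table: "All reported treatment-emergent adverse events will be included in the analysis", so the event is tabulated under its own coded term. That gives counts term by term, not the number of subjects with any event of the group.
- Preferred-term clusters: the list is open-ended, so a pigment or eye cluster could be added. None is named, and the clusters are separate from the AESI table.
- Dermatological examination (SAP 6.4.6): results at screening, Month 12 and endpoint, with a listing of subjects who go from normal to abnormal. This covers some skin findings and is not linked to the AESI table.

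**3. What the table counts**

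For one arm, let D be the number of subjects with at least one qualifying event, u the fraction of these with no event marked, and f the number of subjects without a qualifying event who are marked in error.

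Subjects reported = D × (1 − u) + f

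- With u = 0 and f = 0 the table is right.
- With u > 0 and f = 0 it is too low by the fraction u.
- With both above zero the error is f − D × u, which can have either sign.
- u is defined on subjects, not events: a subject with one marked and one unmarked event is still counted.
- If u is the same in all arms and f = 0, the difference in incidence between arms shrinks by the factor (1 − u) and the ratio is unchanged.

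The documents give none of D, u and f. For scale only: 557 subjects were randomized (SAP Section 1), so with equal arms 557 / 3 ≈ 186 per arm, and each subject missed lowers an arm's incidence by 1 / 186 ≈ 0.54 percentage points. This does not estimate how many are missed.

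**4. Scope of the eye category**
- Protocol 12.3.3 and Attachment 2: ophthalmologic adverse events, without restriction.
- SAP 6.1: retinal changes, with iris colour under hypopigmentation.

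The SAP introduces its groups with a word that could allow others, but it names no category for the remaining eye events.

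**The case against.** The strongest reply is that the SAP counts these events as the protocol collects them, so there is no conflict over the mark itself. Protocol 11.10 promises no more than a possible count or listing. This stands: a term list is an improvement, not the repair of a contradiction. The hepatic query is not proof of inconsistency either. Raised liver enzymes are handled in the protocol as an adverse drug reaction (12.3.4) and are not on its AESI list, so a query is the natural tool there.

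The second reply is that ascertainment rests on more than a tick box. Initial reports of these events must reach the sponsor within 24 hours even when not serious (12.3.3). Attachment 2 asks for dermatological consultation and photographs for lightening of skin or hair, and for contact with the medical monitor about eye events. This also stands, and it makes missed marks less likely. It does not add a missed event to the table, because no step links those reports to the mark.

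Four stronger readings are tempting but not supported:
- A reader might infer that the data are lost. They are not, as the general table shows.
- A reader might infer that AESI incidence must be biased downward, or by a stated percentage. Over-marking is possible, and no rate of missed marks is given.
- A reader might infer from the AESI text added by Amendment 4 that earlier events went unmarked. The Amendment 2 entry already describes recording and expedited reporting of these events, and no document says the mark was absent before Amendment 4.
- A reader might infer that eye events carry the same BACE-2 rationale as pigment change. Protocol 1.4 ties BACE-2 to fur discoloration and reports no relevant eye changes. The Amendment 2 entry attributes the eye AESI to a recommendation from the Voluntary Harmonisation Procedure.

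**Conclusion.** The point holds in a limited form. As written, a hypopigmentation or retinal event enters the AESI incidence table only if the investigator marked it, and a qualifying coded event without the mark is absent from that table alone. The size of any undercount cannot be estimated from the documents, and the net direction of error is not established because marks may also be applied too freely. The SAP's eye content is also narrower than the protocol's AESI, and that difference is plain on the page.

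The conclusion assumes that the SAP sentence on investigator identification is the full rule, since neither document supplements it. The change is worth making because it is cheap and makes the table's completeness visible. The general adverse event analysis is not in doubt.

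**What to change.** In SAP 6.1 Adverse Events:
- Define each AESI as an event marked by the investigator **or** coded to a preferred-term list fixed before unblinding. Use skin and hair hypopigmentation terms for the first group, and eye terms that match the protocol's ophthalmologic AESI for the second.
- Base the incidence table on the union, counting subjects.
- Footnote the counts by route: marked only, coded only, both.

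The cost is one term list reviewed blind and a few lines of programming, with no new data. The downside is that the list may pick up some non-specific terms; the counts by route will show how many. If every qualifying event was marked, the footnote will show that too.

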6.1. Clinical Laboratory Tests

Clinical laboratory blood samples will be collected at screening; at randomization; after randomization every 2 weeks through Month 3, then monthly through Month 6, then every 2 months through Month 12, then every 3 months through Month 54 (or early termination). Urinalysis samples will be collected at screening and after randomization at Months 12, 27, 42, and 54 (or at early termination).

Creatinine clearance will be calculated using the Cockcroft-Gault equation:

$$\frac{(140 - age) * wt}{72 * (CRT/88.4)} [* 0.85, \text{ if female}]$$

Where *age* is age, *wt* is body weight in kg on the date of the laboratory sample (or on the most recent prior visit), and *CRT* is creatinine in $\mu\text{mol/L}$.

Descriptive statistics will be presented for all chemistry, hematology, and urinalysis (pH and specific gravity) laboratory parameters at scheduled time points for on-treatment period.

Change from baseline to each time point and the endpoint in the on-treatment period will be summarized for chemistry, hematology, and urinalysis (pH and specific gravity) parameters and displayed by treatment group.

Shift tables, by treatment group, will be provided summarizing the shift in laboratory values from baseline to each time point and to the endpoint in the on-treatment period with respect to the central laboratory reference ranges (low, normal, high).

Number and percentage of subjects with post-baseline potentially clinically important laboratory values will be presented by treatment group. Definitions of potentially clinically important laboratory values are provided in [Attachment 6](#).

All above summaries will also be presented for the off-treatment period.

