### 4.1. Inclusion Criteria

Each potential subject must satisfy all of the following criteria to be enrolled in the study.

1. Subject must be a man or woman 60 to 85 years of age, inclusive, at time of informed consent. Subjects 60 to 64 years of age must also have 1 of the following 3 conditions:
  - a. A positive family history for dementia (minimum of 1 first degree relative)
  - b. A previously known *APOE*  $\epsilon$ 4 genotype
  - c. A previously known biomarker status demonstrating elevated amyloid accumulation in CSF or PET
2. Subjects must have a global CDR score of 0 at screening.
3. Subjects must be able to read and write and must have adequate hearing and visual acuity to complete the psychometric tests. The legally acceptable representative must also be able to read and write.
4. Subjects must have evidence of elevated amyloid accumulation by means of either:
  - a. Low CSF  $A\beta_{1-42}$  levels at screening
  - b. A positive amyloid PET scan at screening (depending on the site's PET capability)

*Note: The cut-off value for CSF  $A\beta_{1-42}$  will be based on the value established by the central CSF screening laboratory and specified in a separate laboratory manual. Screening amyloid PET scans will be assessed centrally by a qualified reader for inclusion based on predefined criteria as documented in the imaging manual.*
5. Subjects must be otherwise healthy for their age group or medically stable with or without medication on the basis of physical examination, medical history, vital signs, and 12-lead ECG performed at screening or at baseline.
6. Subjects must be otherwise healthy or medically stable on the basis of clinical laboratory tests performed at screening. If the results of the serum chemistry panel, hormones (thyroid tests), hematology, or urinalysis are outside the normal reference ranges, the subject may be included only if the investigator judges the abnormalities or deviations from normal to be not clinically significant, to be appropriate and reasonable for the population under study, and not to be a potential cause of cognitive impairment. For low vitamin B12 and abnormal thyroid hormone tests, enrollment requires written approval from the sponsor's medical monitor.

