6.2. Vital Signs

Blood pressure, pulse, and body temperature will be measured at screening; at randomization; every 3 months after randomization through Month 12, then every 6 months through Month 54 (or early termination). At each visit, blood pressure and pulse will be measured in both supine and standing positions. Weight will be measured at screening; at randomization; then every 6 months after randomization through Month 54 (or early termination). Height will be measured at screening and Month 54 (or early termination).

Continuous vital sign variables including pulse, blood pressure (systolic and diastolic), temperature, weight, and Body Mass Index (BMI) will be summarized with descriptive statistics at each on-treatment time point and for the on-treatment endpoint. BMI will be calculated as $[\text{weight (kg)} / (\text{height (m)})^2]$ at each time point that body weight is measured. The height measurement collected at screening will be used in the calculation. Changes from baseline will be summarized for each on-treatment time point and for the on-treatment endpoint. Descriptive statistics (mean, standard deviation, median, minimum and maximum) will be presented. Weight will be plotted over time for the on-treatment period and for the off-treatment period.

Incidence of treatment-emergent potentially clinically important abnormalities in vital signs while on treatment, as defined in [Table 4](#), will be summarized for subjects who had a baseline assessment and at least one post-baseline, on-treatment assessment for that vital sign. The incidence will also be summarized for the off-treatment visits.

For off-treatment period, the vital sign variables will be similarly summarized.

Table 4: Potentially Clinically Important (PCI) Criteria for Vital Signs

Vital sign	Criteria for Low PCI Values	Criteria for High PCI Values
Systolic BP (mmHg)	< 90	>180
Diastolic BP (mmHg)	<50	>105
Pulse (bpm)	<50	>120
Temperature (C)	<36	>38
Weight (kg)	Decrease of 10% relative to baseline	Increase of 10% relative to baseline
Orthostatic hypotension	A decrease in systolic (>20 mm Hg) or diastolic (>10 mm Hg) blood pressure after standing for at least 2 minutes relative to supine position with an increase in pulse rate of >15 beats per minute.	

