6.3. Electrocardiogram (ECG)

ECGs will be performed at screening; at randomization; after randomization at Month 1, Month 3, and Month 6; then, every 6 months through Month 54 (or early termination).

The ECG variables that will be analyzed are heart rate, PR interval, RR interval, QRS interval, QT interval, and QTc using the following correction methods:

- Bazett's formula: $QTcB \text{ (msec)} = QT \text{ (msec)} / (60/HR(\text{bpm}))^{1/2}$;
- Fridericia's formula: $QTcF \text{ (msec)} = QT \text{ (msec)} / (60/HR(\text{bpm}))^{1/3}$;
- Linear Derived formula: $QTcLD(\text{msec}) = QT(\text{msec}) + \beta * (1-60/HR(\text{bpm}))$, where β is the estimated slope derived from the linear regression model $QT(\text{msec}) = \alpha + \beta * 60/HR(\text{bpm})$ using all observations prior to treatment initiation of all subjects excluding screen failures;
- Sagie formula: $QTcI \text{ (msec)} = QT(\text{msec}) + 154 * (1 - 60/HR(\text{bpm}))$

QTcB and QTcF will be provided by the central ECG vendor and not recalculated. Triplicate ECGs, completed within a 4-minute time period, are collected at each visit. The value for each parameter on a given date will be the average of the values obtained from the triplicate ECGs.

Descriptive statistics will be presented by treatment group for the above ECG variables at each scheduled time point and for the on-treatment endpoint. Change from baseline to each scheduled on-treatment time point and to the on-treatment endpoint will be descriptively summarized by treatment group. For off-treatment visits, change from the off-treatment baseline (see Section 2.4) will also be calculated.

The number and percentage of subjects with treatment-emergent potentially clinically important ECG values as defined in [Table 5](#) below will be presented for each on-treatment time point by treatment group.

Table 5: Potentially Clinically Important (PCI) Criteria for Selected ECG Parameters

Parameter	Criteria for Low PCI Values	Criteria for High PCI Values
HR	< 50	> 100
PR	< 120	> 200
QRS	< 70	> 120
QT		> 500

The number and percentage of subjects with corrected QT values within each of the categories defined below will be presented for the maximum post-baseline, on-treatment value and for each on-treatment time point by treatment group.

- QTc Interval:
 - Males
 - ≤ 450 msec
 - > 450 to ≤ 480 msec
 - > 480 to ≤ 500 msec

- >500 msec
- Females
 - ≤ 470 msec
 - >470 to ≤ 500 msec
 - >500 msec
- QTc change from baseline
 - ≤ 30 msec

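### The laboratory PCI table in SAP 6.1 has no baseline condition, so values beyond a limit before the first dose, or carried over into the off-treatment period, count as cases

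*SAP*

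**What the plan says.** SAP 6.1 (Clinical Laboratory Tests) defines the table in one sentence: "Number and percentage of subjects with post-baseline potentially clinically important laboratory values will be presented by treatment group". It refers to Attachment 6 for the limits and repeats the summary for the off-treatment period. All limits in Attachment 6 are fixed values or multiples of ULN, except that the low hemoglobin criterion also has a change-from-baseline part.

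The neighbouring sections are worded differently:

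- **Vital signs (SAP 6.2):** "Incidence of treatment-emergent potentially clinically important abnormalities in vital signs while on treatment" are summarized, for "subjects who had a baseline assessment and at least one post-baseline, on-treatment assessment for that vital sign".
- **ECG, Table 5 (SAP 6.3):** "The number and percentage of subjects with treatment-emergent potentially clinically important ECG values" are presented.
- **QTc categories (SAP 6.3):** "The number and percentage of subjects with corrected QT values within each of the categories defined below will be presented for the maximum post-baseline". That is the highest result while on drug, with no baseline condition.
- **Liver tests (SAP 6.1.1):** PCI percentages based on change from baseline are added for ALT, AST, alkaline phosphatase, total bilirubin, lymphocytes and eosinophils. The off-treatment liver criteria are limited to subjects within the normal range at the off-treatment baseline.

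The word treatment-emergent is not defined for vital signs or ECG. For adverse events the SAP defines it by timing: "Any AE occurring on or after the date of the initial administration of study medication through the day of last dose plus 7 days". For the C-SSRS (SAP 6.4.2) it means an increase from baseline, and the denominator is restricted by the baseline criterion.

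On entry, Protocol inclusion criterion 6 says of laboratory results outside the reference ranges that "the subject may be included only if the investigator judges the abnormalities or deviations from normal to be not clinically significant" (further conditions follow).

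**The concern.** An incidence table by arm should show what happens after treatment starts. Followed literally, the SAP 6.1 sentence also counts a subject whose value was beyond the limit before the first dose and did not move. Randomization spreads such subjects evenly in expectation, so they add a similar background count to each arm. The ratio between arms then moves towards 1, although no arm is favoured.

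The off-treatment version has a different problem. SAP 2.4 sets the off-treatment baseline equal to the last on-treatment result. An elevation that arose on treatment and persists after the last dose is counted again as an off-treatment case. That carry-over need not be equal across arms. SAP 6.1.1 guards its own off-treatment liver criteria against this; the SAP 6.1 table does not, so the two would handle the same enzymes in the same period by different rules.

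**Working it through.** The plan states no figure for this table, so there is nothing to reproduce. The check is a formula applied to assumed rates.

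**Inputs (all assumptions; the documents give none of them):** b = proportion beyond the limit at baseline, equal in both arms; s = probability that such a subject is also beyond the limit after baseline; p = new-onset risk among the rest.

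**Formulas**

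- Rate as SAP 6.1 is written = b·s + (1 − b)·p
- Rate with a baseline condition = p, at any b
- Risk difference as written = (1 − b)·(p_active − p_placebo), because b·s cancels

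**Scenario 1:** p = 2% placebo, 10% active; s = 80%. With a baseline condition: ratio 5.0, difference 8.0 points.

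- b = 10%: placebo 0.08 + 0.90 × 0.02 = 9.8%; active 0.08 + 0.90 × 0.10 = 17.0%. Ratio 1.7, difference 7.2 points.
- b = 30%: placebo 0.24 + 0.70 × 0.02 = 25.4%; active 0.24 + 0.70 × 0.10 = 31.0%. Ratio 1.2, difference 5.6 points.

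**Scenario 2:** p = 3% placebo, 10% active; s = 100%. With a baseline condition: ratio 3.33, difference 7.0 points.

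| b | Ratio as written | Difference as written (points) |
|---|---|---|
| 1% | 2.75 | 6.9 |
| 5% | 1.85 | 6.7 |
| 10% | 1.50 | 6.3 |
| 20% | 1.25 | 5.6 |
| 40% | 1.10 | 4.2 |

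The ratio is sensitive to b. The difference shrinks only by the factor (1 − b).

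**Which rows could have a large b?**

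- *Hepatic rows.* ALT, AST, alkaline phosphatase, bilirubin and GGT have limits of >3 ULN. Exclusion criteria 18 and 22 remove clinically significant ongoing hepatic conditions and clinically active liver disease. Protocol 9.9.6 asks that hepatic enzyme elevations be explained and shown to normalize. On-treatment b should be near zero.
- *Limits near normal values.* Glucose >5.6 mmol/L and sodium <135 or >145 mmol/L are examples. Subjects are 60 to 85 years old, and Amendment 4 removed the fasting requirement for laboratory tests. A sizeable b is plausible here but not documented.

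**Off-treatment table.** The formula is the same, but b is now the proportion beyond the limit at the last on-treatment value and can differ by arm. As an illustration only, take b = 2% placebo and 10% active, s = 80%, and the same new off-treatment risk of 2% in both arms. Placebo: 0.02 × 0.80 + 0.98 × 0.02 = 3.6%. Active: 0.10 × 0.80 + 0.90 × 0.02 = 9.8%. The table shows a ratio of about 2.8 (0.098/0.0356) with no difference in new off-treatment onset. The distortion can therefore run opposite to the on-treatment one.

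**Do other outputs correct the percentages?** The shift tables in SAP 6.1 refer to baseline but use the reference ranges, not the PCI limits. The listing in SAP 6.1.1 shows all values over time for subjects with a clinically important value, so a reader can see individual baselines, but the table is unchanged. The change-from-baseline PCI summary in 6.1.1 covers six tests, and Attachment 6 gives no change criterion for any of them.

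**The case against.** The strongest case against has four parts.

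1. *The vital-sign and ECG rules may not differ in substance.* A reader might infer that SAP 6.2 and 6.3 exclude subjects already beyond the limit. The SAP does not say so. The vital-sign rule requires only that a baseline assessment exists, and the QTc categories carry no baseline condition. This stands. What remains is a difference in wording, with the C-SSRS rules and the off-treatment liver criteria showing that the SAP conditions on baseline where it chooses to.

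2. *The study was stopped for hepatic safety, and that signal is handled elsewhere.* A reader might infer that the on-treatment hepatic signal is diluted. The documents do not support this. The limits are far from normal, entry was screened, and 6.1.1 adds threshold counts, time-to-event curves and eDISH plots. This stands for the on-treatment rows but does not answer the off-treatment carry-over for ALT and AST.

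3. *Criterion 6 concerns reference ranges, not PCI limits.* This is correct. It shows that out-of-range values do not bar entry, not how many subjects exceed a PCI limit. Where a limit lies near normal values the gap between the two is small; for >3 ULN it is wide.

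4. *Safety summaries are descriptive and the arms are balanced by randomization.* This also stands: no test is distorted, no arm is favoured on treatment, and risk differences move much less than ratios. The percentages are still what a reader will compare.

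**Conclusion.** The point holds for one output: the laboratory PCI incidence table in SAP 6.1, on and off treatment. On treatment the ratio between arms is pulled towards 1, and the difference shrinks by the factor (1 − b). The effect is probably negligible for the >3 ULN hepatic limits and could be material for limits near normal values. The sizes rest entirely on assumed prevalence, persistence and risks. Off treatment, persisting on-treatment elevations enter the count, including ALT and AST, and the direction of the distortion is not fixed.

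It would be too strong to say that laboratory shifts in general are diluted. The change-from-baseline summaries, the shift tables and the 6.1.1 outputs do not depend on this sentence and are not affected.

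**What to change.** In SAP 6.1, replace the sentence with a count of treatment-emergent PCI values, defined as follows:

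- For each test, handle the low and the high limit separately, so that a subject high at baseline can still be counted for a later low value.
- Case: criterion not met at baseline and met at one or more post-baseline on-treatment values.
- Denominator: subjects not meeting that criterion at baseline who have at least one post-baseline on-treatment value.
- For the off-treatment table, use the off-treatment baseline from SAP 2.4 and off-treatment values.

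State this definition once and apply it to the vital-sign and ECG Table 5 PCI tables, where the term is used without one. Weight needs no baseline flag, because its criterion is already relative to baseline. In SAP 6.1.1, state which change criterion is meant for the six listed tests, since Attachment 6 gives only absolute limits for them.

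The cost is a short text change and a baseline flag per limit in the program. The drawback is a smaller denominator for tests with common baseline abnormality (in the 30% scenario, 30% fewer subjects), so the denominator should be printed with each row.
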